#### **Deteriorating renal function monitoring over time**

Absolute value, change and percentage change from baseline in eGFR (central labs) by visit and treatment

SToI analysis of PTs as described in Appendix C: List of preferred termsC: List of preferred terms. This would include an overall summary table of frequencies of AE, SAEs, DAEs, and a summary table by PT based on a pre-defined list of preferred terms

TP-GDO-WW-016-08 **CONFIDENTIAL** Effective Date: 26 Nov 19 **Project Document Effective Date**: Date of last signature Related to: SOP-GDO-WW-019

The summary will be provided for all the AE with an onset date, or worsening, on or after first dose of investigational medical product (IMP) and within 28 days after last dose of IMP and based on the on-treatment definition when otherwise specified. A summary based by eGFR categories will be also presented.

The incidence of hyperkalaemia, hypotension and deteriorating renal function will be summarized by treatment group.

# 4.11.4 Clinical Laboratory Evaluation

Blood and urine samples for determination of clinical chemistry, haematology, and urinalysis will be taken at the visits indicated in the SoA (Appendix A: Schedule of Activities).

The following laboratory variables will be measured.

**Table 2 Laboratory Safety Variables** 

Haematology/Haemostasis (whole blood) a	Clinical Chemistry (serum or plasma) a
White blood cell (WBC) count	Na +b
Red blood cell (RBC) count	K + b,c
Haemoglobin (Hb)	Blood urea nitrogen (BUN)
Haematocrit (HCT)	Serum creatinine b,d
Neutrophils absolute count f	Uric acid f
Lymphocytes absolute count f	Albumin
Monocytes absolute count f	Calcium
Eosinophils absolute count f	Phosphate
Basophils absolute count f	Alkaline phosphatase (ALP)
Platelets	Alanine aminotransferase (ALT)
International normalised ratio (INR) e	Aspartate aminotransferase (AST)
MCV f	Total bilirubin (TBL)
MCHC f	Glutamate dehydrogenase (GLDH) f
RBC distribution width f	Creatine kinase (CK) f
HbA1c	Bicarbonate (HCO 3 -) f
Urinalysis (urine) a	Chloride (Cl  ) f
Protein	Magnesium (Mg + )
Glucose	Glucose
Blood	Total cholesterol, direct HDL-C, triglycerides, LDL-C g , VLDL-C g (fasting, see Section 5.3.1) f
Leukocyte esterase	Other assessments
Specific gravity f	Cystatin C d, h

Haematology/Haemostasis (whole blood) a	Clinical Chemistry (serum or plasma) a
pH f	RT-PCR test for SARS-CoV-2 (optional, at pre- randomisation visit)
Microscopic examination of the sediment if blood or leukocyte esterase are positive on dipstick f	Follicle stimulating hormone (FSH) (for confirmation of postmenopausal status of women <50 years old only [women who are permanently sterilised are exempted], at screening)

<sup>a Local laboratory at screening and pre-randomization (if applicable per SoA) and central laboratory at subsequent visits, unless specified otherwise.

- At the local laboratories, electrolytes (Na+ and K+) and creatinine may be measured in plasma samples instead of serum samples depending on their capability.
- c Central laboratory measurements for K+ levels will be with serum and plasma samples.
- eGFR (mL/min/1.73 m^2) will be calculated using the BSA adjusted CKD-EPI formula and including both serum creatinine and serum cystatin C for central laboratory assessments, and with serum/plasma creatinine alone for local laboratory assessments. Extended formulas adopted for eGFR calculation are provided in Appendix B.
- The post-randomisation INR measurements may be done at a local laboratory if the necessary material provided by the central laboratory is not available; and the measurements may be omitted if the local laboratory is not capable of doing the measurements. Refer to Laboratory Manual for details.
- These tests are not required at screening or pre-randomization.
- g Per Friedewald equation
- h Central laboratory for all cystatin C measurements.

Laboratory parameters will be presented for each treatment group and/or visit.

The outlier laboratory values based on predefined criteria will be presented by treatment as defined in Table 3. A laboratory value will be considered abnormal if it meets the predefined criteria for the abnormality, except where the baseline value met the criteria for the abnormality and the new value is less extreme than the baseline value. Only the most severe value per participant will be accounted for.

Table 3 Laboratory abnormalities by predefined criteria

Blood Chemistry						
ALP Number of subjects with any on-treatment value >1.5x ULN >3x ULN	Total bilirubin  Number of subjects with any on-treatment value  >1.5x ULN  >2x ULN					
ALT Number of subjects with any on-treatment value >3x ULN >5x ULN >10x ULN >20x ULN	Na + (mmol/L)  Number of subjects with any on-treatment value  <120  <130  >150					

Blood Chemistry						
AST Number of subjects with any on-treatment value >3x ULN >5x ULN >10x ULN >20x ULN	K + (mmol/L)  Number of subjects with any on-treatment value ≤2.5					
ALT or AST  Number of subjects with any on-treatment value  >3x ULN  >5x ULN  >10x ULN  >20x ULN						
Haematocrit						
Haematocrit (Vol)  Number of subjects with any on-treatment value <0.20 >0.55 >0.60	Hemoglobin (g/L) Number of subjects with any on-treatment value <60 >180 >200					

For each scheduled post-baseline visit, descriptive statistics for all clinical chemistry and haematology parameters will be presented for observed values at each visit (including baseline) and change from baseline.

For haematology and chemistry, a shift table will present the baseline assessment against the minimum and the maximum on-treatment category.

Elevation in liver parameters for assessment of Hy's law will be done and reported appropriately if potential cases have been identified during the study.

Key patient information will be presented for patients with treatment-emergent changes in laboratory parameters outside of predefined criteria.

The following summaries will be also provided:

- Baseline versus maximum value on-treatment in each urinalysis laboratory parameter by treatment group (shift table)
- Maximum on-treatment ALT and AST by maximum total bilirubin for assessing Hy's Law criteria
- Treatment emergent haematology abnormalities and chemistry abnormalities by predefined criteria
- A summary of individual participant data for participants with Potential Hy's Law

By-participant listings of all laboratory data for the SS will be provided including participant identifier, treatment, age, sex, race, visit, category for lab test, lab test or examination name, result, standard units, reference range indicator. All values outside the clinical reference ranges will be flagged in the data listings. The abnormal values will be flagged with 'L' for values below the lower limit of the clinical reference range and 'H' for values above the upper limit of the clinical reference range and included in the listings.

The on-treatment definition is described in section 4.11.2.

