Appendix E Actions Required in Cases of Increases in Liver Biochemistry and Evaluation of Hy's Law

E 1 Introduction

This Appendix describes the process to be followed in order to identify and appropriately report potential Hy's law (PHL) cases and Hy's law (HL) cases. It is not intended to be a comprehensive guide to the management of elevated liver biochemistries.

During the course of the study the investigator will remain vigilant for increases in liver biochemistry. The investigator is responsible for determining whether a participant meets potential PHL criteria at any point during the study.

All sources of laboratory data are appropriate for the determination of PHL and HL events; this includes samples taken at scheduled study visits and other visits including central and all local laboratory evaluations even if collected outside of the study visits; for example, PHL criteria could be met by an elevated ALT from a central laboratory **and/or** elevated TBL from a local laboratory.

The investigator will also review AE data (for example, for AEs that may indicate elevations in liver biochemistry) for possible PHL events.

The investigator participates, together with AstraZeneca clinical project representatives, in review and assessment of cases meeting PHL criteria to agree whether HL criteria are met. HL criteria are met if there is no alternative explanation for the elevations in liver biochemistry other than DILI caused by the IMP.

The investigator is responsible for recording data pertaining to PHL/HL cases and for reporting SAEs and AEs according to the outcome of the review and assessment in line with standard safety reporting processes.

E 2 Definitions

Potential Hy's Law (PHL)

Aspartate Aminotransferase (AST) or ALT \geq 3 x ULN together with TBL \geq 2 x ULN at any point during the study following the start of study medication irrespective of an increase in alkaline phosphatase (ALP).

Hy's Law (HL)

AST or $ALT \ge 3 \times ULN$ together with $TBL \ge 2 \times ULN$, where no other reason, other than the IMP, can be found to explain the combination of increases, eg, elevated ALP indicating cholestasis, viral hepatitis, another drug.

For PHL and HL the elevation in transaminases must precede or be coincident with (ie, on the

same day) the elevation in TBL, but there is no specified time frame within which the elevations in transaminases and TBL must occur.

E 3 Identification of Potential Hy's Law Cases

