#### 4.11.2 Adverse Events

All AEs will be recorded from the time of randomisation and SAEs will be recorded from the time of signing the full ICF for the study (Visit 1a). No AE or SAE information will be collected after just signing of the optional pre-screening ICF. Recording of all AEs will continue until the end of the participant's safety follow-up period.

All AEs will be coded using the most recent version of the MedDRA that will have been released for execution at AstraZeneca or designee.

When not otherwise specified only AEs occurring with an onset date, or worsening, on or after first dose of investigational medical product (IMP) and within 28 days after last dose of IMP will be summarized.

The following rules will be used to determine whether or not an AE has taken place on-treatment:

- 1. An AE with an onset date and time on or after the date and time of first dose up to and including 5 days following the date and time of last dose of study treatment will be considered on-treatment
- 2. An AE with an incomplete start date and whose end date is not prior to the time of dosing on Day 1 will be considered to have taken place on-treatment unless the non-missing components of the incomplete start date indicate that the start date falls outside the time from dosing on Day 1 to last dose plus 5 days

The following variables will be collected for each AE:

- Adverse event diagnosis/description (verbatim)
- The date and time when the AE started and stopped
- Maximum intensity
- Whether the AE is serious or not
- Investigator causality rating against the investigational medicinal product AZD9977 and/or the investigational product Dapagliflozin (yes or no)
- Action taken with regard to investigational products (AZD9977 and/or Dapagliflozin)
- Adverse event caused subject's withdrawal from the study (yes or no)
- Outcome

Unless otherwise specified, all summaries will be provided by treatment group for the SS.

The number and percentage of AEs will be presented by SOC and/or PT and for each eGFR category.

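### The SAP's aggregate Hy's law table stops counting ALT/AST 5 days after last dose and gives no window for bilirubin, while the protocol counts potential cases at any point after first dose

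*SAP*

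**What the plan says.** SAP 4.11.4 (Clinical Laboratory Evaluation) lists a summary of "Maximum on-treatment ALT and AST by maximum total bilirubin for assessing" Hy's law criteria and closes with the pointer "The on-treatment definition is described in section 4.11.2". Section 4.11.2 is written for adverse events. An event starting at or after first dose and "up to and including 5 days following the date and time of last dose of study treatment will be considered on-treatment".

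Protocol Appendix E 2 defines a potential Hy's law (PHL) case as AST or ALT at or above 3 x ULN together with total bilirubin (TBL) at or above 2 x ULN, "at any point during the study following the start of study medication". The order matters, since "the elevation in transaminases must precede or be coincident with" the bilirubin rise, but "there is no specified time frame within which the elevations in transaminases and TBL must occur". Appendix E 1 accepts all laboratory sources: scheduled and other visits, central and local.

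SAP 4.11.4 also plans an individual-data summary for participants with PHL, a general statement that potential cases found during the study will be reported, and listings of all laboratory data. None of these three carries an on-treatment limit.

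**The concern.** The only aggregate table meant to assess Hy's law criteria uses a narrower window than the protocol's definition of a case. Liver injury can declare itself after drug is stopped. The protocol provides for this with central chemistry at Visit 11 and, for PHL cases, monitoring under Appendix E 4.2 until values return to normal or baseline, or as long as medically indicated. Those results are collected, but at least the ALT and AST values cannot enter the table once 5 days have passed since last dose.

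The stake is the by-arm liver signal. Hepatotoxicity is a listed potential risk of AZD9977 in the protocol's risk table (Table 2), with monitoring for potential Hy's law cases as the mitigation. Each such case carries a lot of weight, so a table that omits or misplaces one can disagree with the SAE data and with the SAP's own PHL summary. The unstated bilirubin window adds a second problem: two programmers following the SAP could produce different counts.

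**Working it through.** The plan gives no figure to reproduce here. The check is day arithmetic followed by a comparison of rules.

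**Inputs**
- End-of-treatment visit: Day 85 ±3 (Schedule of Activities).
- Last dose: 1 day before that visit (pharmacokinetic sampling note in the Schedule of Activities).
- End of on-treatment window: last dose + 5 days (SAP 4.11.2), applied to sample dates.
- Visit 11: Day 113 ±4, with central chemistry (Schedule of Activities).
- Default adverse event summaries: onset up to 28 days after last dose (SAP 4.11.2).

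**Position of Visit 11**
- Window end = (EOT day − 1) + 5. Nominal: 85 − 1 + 5 = Day 89.
- Gap to Visit 11 = 113 − 89 = 24 days.
- Latest EOT, earliest Visit 11: 88 − 1 + 5 = Day 92; 109 − 92 = 17 days.
- Earliest EOT, latest Visit 11: 82 − 1 + 5 = Day 86; 117 − 86 = 31 days.

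For a participant who completes treatment on schedule, Visit 11 chemistry is therefore always 17 to 31 days outside the window and never enters an on-treatment maximum.

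**Position of Visit 11 against the 28-day SAE window**
- Nominal last dose Day 84; 84 + 28 = Day 112. Visit 11 on Day 113 is 113 − 84 = 29 days after last dose, one day beyond the window.

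**Illustrative cases, last dose Day 84, window closing Day 89**

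| ALT/AST first ≥ 3 x ULN | TBL first ≥ 2 x ULN | PHL under Appendix E | Table, bilirubin unrestricted | Table, bilirubin on-treatment only | Inside 28-day SAE window |
|---|---|---|---|---|---|
| Day 84 | Day 89 | Yes | Counted | Counted | Yes |
| Day 84 | Day 94 | Yes | Counted | Not counted (transaminases only) | Yes |
| Day 90 | Day 94 | Yes | Not counted | Not counted | Yes |
| Day 113 | Day 113 | Yes | Not counted | Not counted | No |

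Rows 3 and 4 fail under either reading, because the limit on ALT and AST is explicit. Row 2 depends on how the bilirubin window is read. The restricted reading is plausible, since Table 3 of the SAP counts bilirubin outliers on on-treatment values only, but the Hy's law line does not say so. For a participant stopped early, the same cut falls 5 days after the actual last dose.

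**The case against.** A reader might infer that all of the SAP's Hy's law reporting is limited to on-treatment values, and that any case completed after drug is stopped is shown as not meeting the criteria. The documents do not support either inference. The PHL participant summary, the general reporting statement and the laboratory listings are unrestricted. A case completed within 5 days of last dose is counted. On the literal wording, a late bilirubin rise after an on-treatment ALT rise is counted too.

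Other points on this side also stand. Every PHL case arising on study drug must be reported as an SAE, and the by-arm SAE tables run to 28 days after last dose, so many late cases would appear there. Protocol 9.4.5.3 asks only that liver elevations be assessed and reported appropriately. Appendix E governs how investigators identify and report cases and does not prescribe a table. The strict greater-than cut-offs in Table 3 belong to single-parameter outlier counts and cannot be attributed to the Hy's law table, for which the SAP states no cut-offs. Further presentation detail is deferred to the TFL shells, which are not among the documents. The protocol's risk table also reports no clinically relevant liver chemistry trends in healthy volunteers or the Phase 1b patients.

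These points narrow the concern without removing it. The SAE tables and the PHL summary do not correct the counts in the table meant to assess the criteria. A nominal Visit 11 detection falls outside the 28-day summaries as well. By-visit descriptive statistics do not pair ALT with bilirubin within a participant.

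**Conclusion.** The concern holds for the aggregate table in SAP 4.11.4 and should be addressed. A participant whose ALT or AST first reaches 3 x ULN more than 5 days after last dose is not counted in it under any reading. One whose ALT or AST qualified on treatment but whose bilirubin reaches 2 x ULN after that point is misplaced under one of two readings, and the SAP does not say which applies.

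The size can be stated only in time: the one scheduled post-treatment liver panel lies 24 days beyond the window nominally, and 17 to 31 days beyond it across the visit windows. That is a span of calendar days and not a proportion of cases. With no liver event rate in the documents, the number of participants affected cannot be computed and may be zero.

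The conclusion assumes that the adverse event rule in 4.11.2 is applied to laboratory sample dates, as the pointer in 4.11.4 implies. It also assumes that the table is produced by arm, in line with that section's statement that laboratory parameters are presented by treatment group and/or visit.

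**What to change.** In SAP 4.11.4, state one window for ALT/AST and TBL in the Hy's law table: all values after first dose through Visit 11, scheduled and unscheduled, central and local. Write in the Appendix E cut-offs (at or above 3 x ULN and at or above 2 x ULN). Flag participants whose qualifying values occurred more than 5 days after last dose, and keep the on-treatment version as a second display.

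A maximum-by-maximum table cannot enforce Appendix E's order condition under any window. A participant whose bilirubin rose first could therefore fall in the cell that meets both cut-offs, and a footnote pointing to the individual PHL summary would deal with this. The SAP already has a follow-up-visit analysis for eGFR in 4.11.3, so looking past the on-treatment window has a precedent within the plan.

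The cost is one extra or re-specified table: SAP wording and data selection, with no new samples and no change to study conduct.

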# 4.11.5 Electrocardiogram

Single 12-lead ECG will be obtained after the patient has been resting in a supine position for at least 10 minutes, at the visits outlined in the SoA (Appendix A: Schedule of Activities).

A digital ECG machine that automatically calculates the heart rate and measures PR, QRS, QT, and QTc intervals will be used. Interpretation of the clinical safety digital ECG findings will be reviewed and confirmed by the investigator and recorded in the eCRF. Digital ECGs will be collected, cleaned, and stored by eResearch Technology (ERT).

Potentially clinically significant (PCS) ECG values will be identified based on the predefined criteria displayed in Table 6

Table 4 PCS ECG predefined criteria

Variable	Unit	Outside lower limit if	Outside upper limit if	AZ extended reference range - low	AZ extended reference range - high	Treatment emergent increase if	Extended treatment emergent increase if
Heart	bpm	<50	>100	<45	>120	NA	NA
rate				<30	>150		
RR	ms	<600	>1200	< 500	>1333	NA	NA
interval				<400	>2000		
PR interval	ms	<110	>220	<100	>240	>40	>60
QRS	ms	<75	>115	<70	>120	>15	>30
QT	ms	<320	>450	<300	>480	>30	>60
					>500		
QTcF	ms	<320	>450*	<300	>480*	>30*	>60*
					>500*	1	
QTcB	ms	<320	>450*	<300	>480*	>30*	>60*
					>500		

ms = milliseconds, bpm = beats per minute: NA= not applicable. Note, no standard criteria are established for treatment emergent increases or decreases in RR intervals or heart rates, or for treatment emergent decreases in PR, QRS or QT/QTc intervals.

Note, lower and upper RR interval limits and low and high RR interval reference ranges (all in ms), represent respectively the upper and lower heart rate limits and high and low heart rate reference ranges (all in bpm).

TP-GDO-WW-016-08 Effective Date: 26 Nov 19 Related to: SOP-GDO-WW-019

**Project Document Effective Date**: Date of last signature
Page 34 of 50

\*Cut-off values for categorical analyses as recommended by ICH E14 (Note, more than one category for high range increases in QT/QTc values).

The following summaries will be provided:

- A summary of the ECG variables and change from baseline in each ECG variable by treatment group and time point
- A summary of ECG assessment (normal/abnormal clinically significant/abnormal not clinically significant), baseline versus last observation on-treatment.
- A summary of the number and percentage of subjects reporting PCS ECG values outside predefined criteria, by ECG parameter, treatment and visit

By-participant listings of ECG results and findings will be provided based on SS.

The on-treatment definition is described in section 4.11.2.

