1.3 Schedule of Activities

Table 1Schedule of Activities

Procedure	Pre- scre enin g	Screeni ng	Start Run-in	Pre- rando- misation	Baseline/ Rando misation			Treatm	ient Pe	riod		EOT/ET a	Safety Follow-u p	Notes	Details in CSP Section or Appendix
Visit ^b	Opti onal	1a	1b	2	3	4	5	6	7	8	9	10	11		-
Week	c	(-8 to -7)* -6 to -5	(-7 to -6)* -5 to -4	-1	1	1	2	3	4	7	10	13	17	* Applies to SGLT2i naïve patients	For details on run-in
Day	c	(-56 to -49)* -42 to -35	(-49 to -42)* -35 to -28	-10 to -3	1	3 ± 1	8 ±2	15 ±3	22 ±3	43 ±3	64 ±3	85 ±3	113 ±4		period see Section 4.1
Informed consent	X	X													Appendix A 3
Local laboratory urine samples for albumin and creatinine	х													Sample according to local clinical practice.	Section 8.2.4
Inclusion and exclusion criteria		Х	Х		X										Sections 5.1, 5.2
Enrolment in RTSM		Х													Section 6.3
Demography, height, smoking history, alcohol consumption		x													Sections 5.1, 5.2
Physical examination, weight		х			X (pre- dose)							Х	х	For site visits only.	Section 8.2.1

Procedure	Pre- scre enin g	Screeni ng	Start Run-in	Pre- rando- misation	Baseline/ Rando misation		ľ	Treatm	ient Pe	riod		EOT/ET a	Safety Follow-u p	Notes	Details in CSP Section or Appendix
Visit ^b	Opti onal	1a	1b	2	3	4	5	6	7	8	9	10	11		
Week	c	(-8 to -7)* -6 to -5	(-7 to -6)* -5 to -4	-1	1	1	2	3	4	7	10	13	17	* Applies to SGLT2i naïve	For details on run-in
Day	c	(-56 to -49)* -42 to -35	(-49 to -42)* -35 to -28	-10 to -3	1	3 ± 1	8 ±2	15 ±3	22 ±3	43 ±3	64 ±3	85 ±3	113 ±4	patients	period see Section 4.1
Medical/ surgical history		Х			Х										Sections 5.1, 5.2
Concomitant medication		Х		Х	Х	Х	Х	Х	Х	х	Х	Х	Х		Section 6.5
Adverse events		SAEs only		SAEs only	X	Х	Х	Х	Х	Х	Х	Х	Х		Section 8.3
Vital signs (blood pressure, pulse rate)		X			X (pre- dose)	x	x	x	x	x	x	X	X	Background treatment for hypertension should be individually optimised and stable for 3 weeks before randomisation (Visit 3); BP assessed for eligibility at Visit 3.	Sections 5.1, 6.5.2, 8.2.2
Digital 12-lead safety ECG		X ^d			X (pre- dose)	X		Х		Х		Х		ECGs to be added as clinically indicated.	Section 8.2.3

Procedure	Pre- scre enin g	Screeni ng	Start Run-in	Pre- rando- misation	Baseline/ Rando misation			Treatm	ient Pe	riod		EOT/ET a	Safety Follow-u P	Notes	Details in CSP Section or Appendix
Visit ^b	Opti onal	1a	1b	2	3	4	5	6	7	8	9	10	11		
Week	c	(-8 to -7)* -6 to -5	(-7 to -6)* -5 to -4	-1	1	1	2	3	4	7	10	13	17	* Applies to SGLT2i naïve	For details on run-in period see

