9.4.5.4 Electrocardiograms

Descriptive statistics will be produced at each schedule assessment timepoint for all quantitative ECG parameters (heart rate, PR, RR, QRS, QT, and QTcF intervals) for both observed absolute values and changes from baseline.

Electrocardiogram findings will also be listed.

An analysis of potentially clinically significant ECG values on QT, QTcF, QRS and PR interval, and heart rate will be performed. The number and percentage of patients with potentially clinically significant ECG values will be tabulated across time and treatment group. The criteria based on severity will be defined in the SAP.

Outliers with respect to QTcF will also be tabulated for the following categories:

- Absolute value > 450 ms
- Absolute value > 480 ms
- Absolute value > 500 ms

- Increase from baseline > 30 ms
- Increase from baseline > 60 ms

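### The ECG shift table uses the last on-treatment assessment, not the worst, and outliers are counted only by visit, so participants ever abnormal on treatment cannot be counted

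*SAP*

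**What the plan says.** SAP 4.11.5 plans three ECG summaries. The first gives values and changes by treatment and time point. The second is the overall assessment: "A summary of ECG assessment (normal/abnormal clinically significant/abnormal not clinically significant), baseline versus last observation on-treatment". The third is the outlier count: "A summary of the number and percentage of subjects reporting PCS ECG values outside predefined criteria, by ECG parameter, treatment and visit". The section takes its on-treatment window from SAP 4.11.2, which runs from first dose to 5 days after last dose.

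The Schedule of Activities (Protocol 1.3) puts on-treatment ECGs at Visits 4, 6, 8 and 10 and adds "ECGs to be added as clinically indicated". Protocol 9.4.5.4 says that PCS values "will be tabulated across time and treatment group". It separately asks for QTcF outliers above 450, 480 and 500 ms and for increases above 30 and 60 ms, without saying whether these are by visit or per participant.

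Other safety data in the SAP are handled differently. For laboratory outliers, SAP 4.11.4 says: "Only the most severe value per participant will be accounted for". For shifts it says: "For haematology and chemistry, a shift table will present the baseline assessment against the minimum and the maximum on-treatment category". Urinalysis is shifted from baseline to the on-treatment maximum. SAP 4.11.6 counts notable vital-sign changes by parameter and treatment group, with no visit split.

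**The concern.** A safety shift table is normally meant to show whether anyone got worse on treatment. A last-observation table answers a narrower question: who was abnormal at the end. A by-visit outlier table shows how many were abnormal at each visit, but not how many people that was.

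This matters here because Protocol Table 2 lists cardiovascular effects as a potential risk of AZD9977 and gives monitoring of heart rate, blood pressure and ECGs as the mitigation. Hyperkalaemia is a safety topic of interest, and Protocol Appendix F 1 provides for corrective action and for interrupting or stopping treatment. An ECG change around such an episode could have resolved before the last on-treatment ECG. In addition, exclusion criterion 9 sets no numerical QTc limit, so the number of participants per arm who ever cross a QTcF threshold is a natural question. No stated table answers it. The SAP gives no reason for treating ECG differently from laboratory data and vital signs.

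**Working it through.** The plan has no figure to reproduce, because the point concerns how tables are built.

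**Inputs.** Four scheduled on-treatment ECGs (Visits 4, 6, 8 and 10; Protocol 1.3). About 125 participants per arm (SAP 4.13). The per-visit abnormality rates below are assumptions; the documents give none.

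**1. The rules side by side.**

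| Data | Shift from baseline | Outlier count |
|---|---|---|
| Chemistry, haematology | to minimum and maximum on treatment | any on-treatment value, most severe per participant |
| Urinalysis | to maximum on treatment | – |
| Vital signs | – | per participant, by parameter and treatment |
| ECG | to last on treatment | by parameter, treatment and visit |

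**2. The shift table.** An assessment that is abnormal at Visit 4, 6 or 8 and normal at the last on-treatment ECG appears as normal. Suppose each of four ECGs is abnormal with probability p, independently. The share ever abnormal is 1 − (1 − p)^4, and the share of those who look normal at the last ECG is 1 − p / [1 − (1 − p)^4].

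| p (assumed) | Ever abnormal | Per arm of 125: ever | Per arm: at last | Ever abnormal but normal at last |
|---|---|---|---|---|
| 0.5% | 1.985% | 2.48 | 0.625 | 74.8% |
| 1% | 3.94% | 4.93 | 1.25 | 74.6% |
| 2% | 7.76% | 9.70 | 2.50 | 74.2% |
| 5% | 18.55% | 23.19 | 6.25 | 73.0% |

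Independence within a person is unlikely. If every abnormality persists to the last ECG, the missed share is 0%.

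**3. The by-visit PCS table.** From visit counts alone, the number of distinct participants lies between the largest single-visit count and the sum of the counts. With 2 of 125 at each of four visits:

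- same people each time: 2/125 = 1.6%
- different people each time: (2 + 2 + 2 + 2)/125 = 8/125 = 6.4%

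The printed table is identical in both cases.

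**4. Unscheduled ECGs.** The SAP gives no visit window and no rule for assigning them. By its wording, such an ECG enters the shift table only if it is the last on-treatment observation. Its place in the by-visit table is not stated.

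**The case against.** The strongest reply is that little is really lost, and several parts of it stand.

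- **Scheduled outliers are shown.** A reader might infer that a transient abnormality vanishes from the tables. The documents do not support that for numerical values: an outlier at Visit 4, 6 or 8 is counted at that visit. If 8 participants were each abnormal at one of the four visits, evenly spread, the by-visit table would show 2 + 2 + 2 + 2 and all 8 would be there. A drop from 6.4% (8/125) to 1.6% (2/125) would apply only to the overall-assessment shift.
- **Clinically relevant findings have another route.** Protocol 8.2.3 requires clinically relevant new or worsened ECG findings to be recorded as adverse events, which are tabulated per participant. All ECG results are listed.
- **The main signals are partly covered elsewhere.** Pulse outliers have a participant-level count (SAP 4.11.6), as do potassium thresholds (SAP 4.11.3).
- **Abnormalities need not be gone by the last ECG.** A reader might assume that they are. The documents do not say so. The schedule includes an early-termination ECG, and that ECG or a triggered one may be the last on-treatment observation.
- **Neither table is shown to omit triggered ECGs.** That would be an inference from silence. SAP 4.2 leaves further presentation details to the table shells, which are not available here.

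What the reply does not remove: listings give no rate by arm, and under Protocol 8.3.5 an ECG deterioration becomes an adverse event only if it is serious, leads to discontinuation or is judged clinically relevant by the investigator. Predefined outlier counts are useful because they do not depend on that judgement. The unrestricted QTcF sentence in Protocol 9.4.5.4 does not help either, since the only outlier count that the SAP states for it is by visit.

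**Conclusion.** The concern holds in a limited form. As written, SAP 4.11.5 has three gaps:

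1. A transient abnormal overall assessment that is normal at the last on-treatment ECG is absent from the shift table.
2. The number of participants ever meeting a PCS or QTcF criterion cannot be derived from the planned counts.
3. Unscheduled ECGs have no stated place in the PCS table.

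The second gap follows from the table layout alone: in the example the rate could be anywhere from 1.6% to 6.4%. The size of the first is not known from the documents. Under the illustrative assumption of independent abnormalities at equal rates, about three quarters of ever-abnormal participants would look normal in the shift table; with full persistence, none would. The third is an open question, not a demonstrated exclusion.

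This is a safety-reporting weakness that departs from the SAP's own practice for laboratory data and vital signs. It does not affect the primary analysis.

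**What to change.** In SAP 4.11.5:

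- Replace the last-observation shift with baseline versus the worst on-treatment overall assessment, or add the second beside the first.
- Above the by-visit rows of the PCS table, add one row per criterion in SAP Table 4 for any on-treatment value, scheduled or unscheduled, counting each participant once. Include QTcF above 450, 480 and 500 ms and increases above 30 and 60 ms.
- State that unscheduled ECGs within the on-treatment window feed both.

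The cost is SAP wording, matching changes to the table shells and some extra output. The ECGs are already collected. Ever-abnormal rates will tend to look higher than last-observation rates in all arms, so the text should say which is being reported. Keeping the by-visit rows lets a reader separate scheduled findings from triggered ones.
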